### **3.0 Inclusion/Exclusion Criteria**

Inclusion:

- Men and Women age 18-30 years old
- No current use of mouthwash

Exclusion:

- Men and Women <18 or >30 y of age
- Unable to provide informed consent
- Current users of mouthwash
- Current antibiotic use
- Current smokers
- Stage II hypertension (resting blood pressure >140/>90)

An answer of yes to any of the seven questions on the first page of the Physical Activity Readiness Questionnaire (PAR-Q) indicating that the subject is not physically ready for exercise without a medical exam. These exclusions include the following:

- If participant's doctor has ever said that he/she has a heart condition and that he/she should only do physical activity recommended by a doctor
- Pain in chest when doing physical activity
- In past month, chest pain when not doing physical activity
- If participant has ever lost balance because of dizziness or has ever lost consciousness
- Bone or joint problem that could be made worse by change in physical activity
- Currently on prescribed drugs for blood pressure or heart condition.
- If the participant knows of any other reason why he/she should not do physical activity.

Session exclusion criteria:

- These criteria do not apply to the first study visit, only for visits 2 and 3. Subjects will be instructed to not smoke, perform exercise on the day of the visit, and to not attend the visit in a fasting or hungry state. They will also be asked to not consume caffeine or alcohol or use chewing gum in the 24 hours prior to the visit. They will be asked to avoid consuming foods (e.g., spinach, beets, collard greens) high in NO3 during the evening prior to visits. Subjects will also be instructed to not use any other mouthwash products other than those provided during the study. Subjects will be excluded from a session if their resting blood pressure is greater than 140/90.

[figure not shown]
### **4.0 Enrollment/Randomization**

Study participants will be given a consent form ahead of the screening visit. The study participant will be given time to review the consent form, and a study staff member will contact the potential subject to answer any questions they may have. If interested, then the potential subject will be scheduled for a meeting where the consent form will be reviewed again. The potential subject will be given as much time

as they wish to consider participation before signing the consent form and if they wish to move forward with participating, then the consent form will be signed by both the study participant and the person who reviewed the consent and obtained the participant's signature. A copy of the signed consent form will be provided to the subject. Both the participants and the investigators will be blinded to the order of treatment, which will be randomized in four blocks of four using randomization.com.

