## 2.0 Rationale and Specific Aims

**Specific Aim #1:** To determine the effects of antibacterial mouthwash on maximal knee extensor speed and power in healthy young men and women.

We hypothesize that use of an antibacterial mouthwash will significantly reduce maximal knee extensor speed and power (primary endpoints). This will be accompanied by significant reductions in salivary  $\text{NO}_3^-/\text{NO}_2^-$  and breath NO levels (secondary endpoints).

We will test these hypotheses using isokinetic dynamometry and salivary and breath sampling in **n = 24** healthy young men and women (n = 8/group).

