## 5.0 Study Procedures

### Study Design

**Figure 1. Overall study design.**

### Study Procedures

**Study Visit 1** (Screening and muscle function testing practice): The consent statement will be reviewed with the subject including the procedures of the study and the risks of participating. Subjects will also be instructed on the requirements while in the study including not exercising on the day of study visits prior to the visit and to not attend the visit in a fasting or hungry state. They will also be asked to not consume caffeine or alcohol or use chewing gum in the 24 hours prior to the visit. They will be asked to avoid consuming foods (e.g., spinach, beets, collard greens) high in  $\text{NO}_3^-$  during this 24 hour period and to not use any other mouthwash products other than those provided during the study. Subjects who decide to participate will sign the consent and complete a screening to determine if they are eligible. If they are determined to be eligible they will then be asked to practice the muscle function test that will be used during the study that assesses the contractile function, i.e., maximal knee extensor speed and power, of the knee extensors of the subject's dominant leg. This is done using a Biodex 4 Isokinetic Dynamometer (Biodex Medical Systems, Shirley, NY).

**Study Visit 2** (Baseline Testing): participants will be asked to return and undergo baseline testing. This will include 1) collection of a saliva sample for a measurement of  $\text{NO}_3^-$  and  $\text{NO}_2^-$ , and, 2) assessment of the muscle function of the knee extensors (see Study Methods). The subjects will then be randomly assigned (via randomization.com) in four blocks of four subjects each to receive either an antibacterial mouthwash (Cepacol®, Reckitt Benckiser, Parsippany, NJ) or, as a control solution, an alcohol-free "natural" mouthwash (Tom's of Maine®, Kennebunk, ME). Participants will be asked to rinse their mouth as directed on the product's packaging for 30 s twice per day for 7 days and to record the usage of the mouthwash on a provided form. Subjects will then return for Study Visit 3. Note that although the two products differ significantly in terms of packaging, color, taste, etc., the subjects will be told that the study is simply to compare the two products, with no expectation as to the outcome.

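### With a fixed, published block size of four and no described concealment, up to one third of assignments could be deduced before the Visit 2 baseline test by staff who see which products are dispensed

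*Combined protocol and SAP*

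**What the plan says.** Section 4.0 (Enrollment/Randomization) states: "Both the participants and the investigators will be blinded to the order of treatment", and continues "which will be randomized in four blocks of four using randomization.com". Since each participant receives only one product, I read order of treatment as meaning assignment.

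Section 5.0, Study Visit 2, puts the saliva sample and knee extensor test first and then says: "The subjects will then be randomly assigned (via randomization.com) in four blocks of four subjects each". The alternatives are an antibacterial mouthwash and a control mouthwash. The same paragraph concedes that "the two products differ significantly in terms of packaging, color, taste, etc", and it has participants follow the directions on the product's packaging. Consent, eligibility screening and the practice test all take place at Visit 1.

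No section says who generates, holds or releases the list, who hands out the mouthwash, whether it is repackaged, or whether the people who book and test participants are kept apart from dispensing.

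Section 2.0 gives a total of 24 "healthy young men and women (n = 8/group"). Four blocks of four supply 16 places, as do two arms of 8.

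**The concern.** Assigning after the baseline test protects the baseline only if the next assignment cannot be foreseen. Here the block size is small, constant and printed where all staff can read it. Once two participants in a block have received the same product, the rest of that block is determined. Hiding the list does not prevent this, because the deduction uses past dispensing and the block size, not the list.

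The primary endpoints, maximal knee extensor velocity and power, come from voluntary maximal efforts (section 5.0, Study Methods), and the hypothesis is directional (section 2.0). Someone who foresees the next product could, without intending to, influence which waiting participant is booked next for Visit 2, or encourage the baseline effort more or less strongly. Either would enter the between-arm comparison. With 8 per group, each participant carries one eighth of an arm's mean.

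**Working it through.** The plan gives no figure for predictability, so there is none to reproduce.

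**Inputs**
- Block size 4, four blocks: sections 4.0 and 5.0.
- Two arms: section 5.0, Study Visit 2.
- 1:1 within blocks (2 + 2): assumption. No ratio is stated; it is inferred from two products and 8 per group.
- q, the share of earlier allocations known to a person who schedules or tests: not given, so taken over the range 0 to 1.

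**Assignments that are certain, q = 1.** A 2 + 2 block has 6 equally likely sequences. An assignment is certain once one arm has used both its places.
- Positions 1 and 2: probability 0.
- Position 3: certain if the first two match, 2/6 = 1/3.
- Position 4: always certain, 1.
- Per block: 0 + 0 + 1/3 + 1 = 4/3, and (4/3)/4 = 33.3%.
- Four blocks (16): 4 × 4/3 = 5.33 on average, range 4 to 8. Six blocks (24): 6 × 4/3 = 8.

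**Best guess, q = 1.** Chances of being right at positions 1 to 4 are 1/2, 2/3, 2/3 and 1. The sum is 2.833, and 2.833/4 = 70.8%, against 50% with no information.

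**Partial knowledge.** If each earlier allocation is known independently with probability q, position 3 is certain with probability q²/3 and position 4 with probability q², since the two matching allocations must both be known. The share is (q²/3 + q²)/4 = q²/3.

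| q | Share certain |
|---|---|
| 1 | 33.3% |
| 0.9 | 27.0% |
| 0.75 | 18.8% |
| 0.5 | 8.3% |
| 0 | 0% |

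**Alternatives, q = 1.** For one balanced list of 2m, the expected number certain is 2m/(m + 1), and the expected number of correct guesses is m + (4^m/C(2m,m) − 1)/2. Putting m = 2 returns 1.333 and 2.833, as above.
- List of 16 (m = 8): 16/9 = 1.78 certain, 11.1%. Correct guesses 8 + (65536/12870 − 1)/2 = 10.05, 62.8%.
- List of 24 (m = 12): 24/13 = 1.85 certain, 7.7%. Correct guesses 12 + (16777216/2704156 − 1)/2 = 14.60, 60.8%.
- Block sizes varied at random with the sequence of sizes undisclosed (simulation, 16 places): about 10% certain with sizes 2 and 4, and about 4% with sizes 2, 4 and 6.

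**The case against.** The strongest reply is the sentence in section 4.0 itself: investigators are to be blinded. If the people who schedule and test never learn what was dispensed, q = 0 and the block size reveals nothing. The remark about packaging, color and taste leads into what participants will be told; it does not say that recruiters or testers see the products. This stands, and it makes one third a ceiling. It does not remove the point, because no mechanism for the blinding is described, staff other than investigators are not mentioned, and the instruction to follow the packaging suggests (without proving) that retail packs reach participants.

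A reader might infer that staff could select who enters the trial. The documents do not support that. Consent and screening are complete at Visit 1, while the place in the sequence is taken only after baseline testing at Visit 2, and anyone randomized in between shifts it. The listed eligibility criteria also leave little room for discretion. Visit 2 booking order and baseline encouragement remain.

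Predictability is also not bias. As an illustration only, suppose full knowledge produced a 5-point arm difference in baseline effort. Acting on certain places alone gives 5 × 1/3 = 1.7 points; acting on every best guess gives 5 × (2 × 0.708 − 1) = 2.1 points. Section 8.0's 8.7% for power, read as an SD, times its effect size of 1.3 gives 11.3 points, so the bias would be about 15% to 18% of the difference the trial is sized to detect, and less if q is below 1. Baseline differences between predictable and unpredictable places could be examined and partly adjusted for, although 16 or 24 participants give little information for that.

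Finally, separating dispensing from scheduling and testing would do most of the work by itself, and would also help with masking at Visit 3. That is fair; the list change is a second safeguard for when that separation fails.

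**Conclusion.** The point holds as a gap in allocation concealment with a calculable ceiling. On average, up to one third of assignments (5.3 of 16, or 8 of 24) could be deduced before the Visit 2 test. This assumes 1:1 blocks, full knowledge of earlier allocations in the block, and no other participant randomized between prediction and assignment. Below full knowledge the share is about q²/3, and the documents give no basis for choosing q.

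The tempting stronger statement, that the design makes a third of assignments certain, is not supported: it would require staff to know every earlier allocation, which the document nowhere says and its blinding statement denies. The effect on the endpoints cannot be sized from the documents. The case for changing the plan is that the weakness is avoidable at almost no cost, which is enough for a should-fix recommendation even in a pilot.

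**What to change.** 1. Reconcile the total of 24, the 8 per group and the 16 block places in sections 2.0, 4.0 and 5.0, since the list length depends on it.
2. In sections 4.0 and 5.0, replace the fixed blocks with a single permuted list of the final N, balanced across the two products, or with varied block sizes that are kept out of the protocol. State the allocation ratio.
3. Name, by role, an existing team member who neither schedules nor tests to generate and hold the list, and say who dispenses the product.
4. Release each assignment only after that participant's Visit 2 dynamometer file has been saved.

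The cost is a few sentences of protocol text and a new list, with no added participants or procedures. The downside is slightly less balance between arms part-way through, or at the end if recruitment stops early.

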## 5.0 Study Procedures

### Study Design

**Figure 1. Overall study design.**

### Study Procedures

**Study Visit 1** (Screening and muscle function testing practice): The consent statement will be reviewed with the subject including the procedures of the study and the risks of participating. Subjects will also be instructed on the requirements while in the study including not exercising on the day of study visits prior to the visit and to not attend the visit in a fasting or hungry state. They will also be asked to not consume caffeine or alcohol or use chewing gum in the 24 hours prior to the visit. They will be asked to avoid consuming foods (e.g., spinach, beets, collard greens) high in  $\text{NO}_3^-$  during this 24 hour period and to not use any other mouthwash products other than those provided during the study. Subjects who decide to participate will sign the consent and complete a screening to determine if they are eligible. If they are determined to be eligible they will then be asked to practice the muscle function test that will be used during the study that assesses the contractile function, i.e., maximal knee extensor speed and power, of the knee extensors of the subject's dominant leg. This is done using a Biodex 4 Isokinetic Dynamometer (Biodex Medical Systems, Shirley, NY).

**Study Visit 2** (Baseline Testing): participants will be asked to return and undergo baseline testing. This will include 1) collection of a saliva sample for a measurement of  $\text{NO}_3^-$  and  $\text{NO}_2^-$ , and, 2) assessment of the muscle function of the knee extensors (see Study Methods). The subjects will then be randomly assigned (via randomization.com) in four blocks of four subjects each to receive either an antibacterial mouthwash (Cepacol®, Reckitt Benckiser, Parsippany, NJ) or, as a control solution, an alcohol-free "natural" mouthwash (Tom's of Maine®, Kennebunk, ME). Participants will be asked to rinse their mouth as directed on the product's packaging for 30 s twice per day for 7 days and to record the usage of the mouthwash on a provided form. Subjects will then return for Study Visit 3. Note that although the two products differ significantly in terms of packaging, color, taste, etc., the subjects will be told that the study is simply to compare the two products, with no expectation as to the outcome.

**Study Visit 3** (Final Testing), participants will be asked to return to undergo the same procedures as described above for Study Day 2.

## Study Methods

*Measurement of Salivary Nitrate & Nitrite:* Saliva samples will be obtained using a salivary sample collection kit (Salivette, Sarstedt, Newton, NC). The  $\text{NO}_3^-$  and  $\text{NO}_2^-$  of each sample will be determined using high performance liquid chromatography (ENO-30, Eicom USA, San Diego, CA).

*Measurement of skeletal muscle contractile functions:* A Biodex 4 System isokinetic dynamometer (Biodex Medical Systems, Shirley, NY) will be used to measure the subject's muscle contractile properties as previously described. Briefly, participants will be asked to perform three maximal isometric knee extensions with their dominant leg at a joint angle of 70 degrees. Each isometric contraction will last 5 s, with 15 s of rest in between. After 2 min of additional rest, the subject will perform three maximal isokinetic efforts at angular velocities of 1.57, 3.14, 4.71, and 6.28 rad/s, with 2 min of rest between each set. To eliminate artifacts, the dynamometer data will be "windowed" to isolate the isokinetic phase and smoothed using a nine point weighted moving average filter, after which the highest torque generated at each velocity will be multiplied by the velocity to determine the peak power at that velocity. The resulting power-velocity data will then be fit with a 2nd order polynomial function (i.e.,  $y=ax^2+bx+c$ ) which will be solved to determine the subject's maximal knee extensor velocity ( $V_{\text{max}}$ ;  $=-b/a$ ) and power ( $P_{\text{max}}$ ;  $=(4ac-b^2)/4a$ ).

## Risks

Likely: Muscle soreness from using the Biodex Isokinetic Dynamometer. Subjects may have muscle soreness in their quadriceps because the quadriceps is responsible for extension of the knee. They might also experience soreness in their knee joint. Fatigue may also be experienced from exercising the muscles.

Very rarely, an exercise test, such as the muscular function test, may be associated with serious complications including, but not limited to:

- Fainting and disorders of the heart beat (too fast or too slow) which may require hospitalization;
- heart attack, stroke, or death.

The risk of arrhythmia and heart attack are rare and the risk of death during exercise testing is extremely rare. The estimated risk of a fatal event during maximal exercise testing ranges from 0.3 to 0.8 per 10,000 tests. Approximately 1.4 nonfatal events occur per 10,000 tests. The risk should be lower in this study as these subjects since they are young, apparently healthy adults have been screened for signs and symptoms of cardiovascular disease.

We will make every effort to minimize these rare risks by observing and monitoring during testing. However, no guarantees can be made.

Mouthwash may cause surface staining of the teeth, an increase in systolic blood pressure, and the taste may be unpleasant to subjects.

Another risk of this study is the possible loss of confidentiality, which is minimal. Even though the risk is small, a link exists between your protected health information and your sample. In addition to the risks listed above, there may be some unknown or infrequent and unforeseeable risks associated with participation in this study. You will be informed in a timely manner of any new information, findings or

changes to the way the research will be performed that might influence your willingness to continue your participation in this study.

There also may be other side effects that we cannot predict.

#### Mitigation of Risks

To minimize the risk of muscle soreness, subjects will warm up by pedaling a stationary cycle for 5 min against minimal resistance.

To minimize the risk of exercise testing, subjects will be screened using an accepted exercise risk screening tool (Physical Activity Readiness Questionnaire - PAR-Q) to ensure subjects are at minimal risk. High risk individuals (those reporting cardiovascular, pulmonary, or metabolic disease) will be excluded from this study.

If any of the following occurs, the subject will be excluded from participating in any test involving physical activity on that day:

- Resting blood pressure systolic > 140 mm Hg or diastolic > 90 mm Hg
- Resting heart rate > 120 beats/min or < 45 beats/min

Blood pressure and heart rate will be taken before and after the isokinetic test.

During exercise testing subjects will be instructed on proper technique including avoiding the valsalva maneuver (holding their breath during exertion) which has been shown to increase blood pressure. Subjects will be instructed that they may stop the tests at any time with no adverse consequences. Subjects will also be instructed to talk with the experimenter about any discomforts that occur during the physical tests. If for any reason the participant reports an injury, chest pain, excessive shortness of breath, abnormal heart rhythm or dizziness, the test will be terminated and they will be referred to their doctor, or the PI will call the doctor or other health care provider.

Additionally, all exercises will occur in an air conditioned facility because environmental extremes can be poorly tolerated during exercise. Also, every precaution will be taken to provide fluids, rest and other measures to insure each participant is comfortable, safe, and secure in the testing/exercise environment. In the unlikely event that an emergency may occur, a CPR certified person will be available for all testing sessions.

To simplify scheduling, the isokinetic muscle assessments will be completed in either *The National Institute of Fitness and Sport* (location of the human performance laboratory), or on an identical system in IU-Health University Hospital, [name], on the 5th floor adjacent to the Clinical Research Center. *The National Institute of Fitness and Sport* has set up provisions to respond to a medical emergency which include: 1) Evaluate the condition of the individual (consciousness, breathing, and pulse), 2) Call 911 or instruct another staff or lab member to call 911 and state "We have an emergency situation at our facility. The individual appears to have (give

condition). Please send a paramedic team to the National Institute for Fitness and Sport located at [name]. We are South of the Natatorium on the IUPUI campus. Someone will meet you at the main entrance to the building." For a life threatening emergency, we are instructed to dial "799" for a NIFS building page. Say "There is a medical emergency in the (given location)." Then hang-up. and 3) initiate CPR procedures if needed. A fully equipped automated external defibrillator is also available in the building. The NIFS emergency procedures will be located in the lab and all research staff will be trained on the emergency procedures. Within the hospital, emergency equipment and trained personnel are available to deal with any emergency.

To minimize the loss of confidentiality, all records will be kept in a locked file cabinet inside an office which has locking doors. All study procedures will be completed behind closed doors inside the Human Performance Laboratory located in the National Institute of Fitness and Sport at [name], or in IU-Health University Hospital, [name], on the 5th floor adjacent to the Clinical Research Center.

## **6.0 Reporting of Adverse Events or Unanticipated Problems involving Risk to Participants or Others**

The following standard definitions will be used for this study:

**Adverse event (AE):** Any untoward or unfavorable medical occurrence in a human study participant, including any abnormal sign (e.g. abnormal physical exam or laboratory finding), symptom, or disease, temporally associated with the participants' involvement in the research, whether or not considered related to participation in the research.

**Serious Adverse Event (SAE):** Any AE that results is place the participant at immediate risk of death from the event as it occurred, or results in inpatient hospitalization, prolongation of existing hospitalization, persistent or significant disability/incapacity, congenital abnormalities or birth defects, or death.

**Unanticipated problem:** As Defined by DHHS 45 CFR part 46, any incident, experience, or outcome that meets all of the following criteria: 1) is unexpected, in terms of nature, severity, or frequency, given (a) the research procedures that are described in the protocol-related documents, such as the IRB-approved research protocol and informed consent document; and (b) the characteristics of the study population; 2) is related or possibly related to participation in the research (in this guidance document, possibly related means there is a reasonable possibility that the incident, experience, or outcome may have been caused by the procedures involved in the research); and 3) suggests that the research places participants or others at a greater risk of harm (including physical, psychological, economic, or social harm) than was previously known or recognized.

AEs will be graded according to the following scale:

- **Mild:** An experience that is transient, and requires no special treatment or intervention. The experience does not generally interfere with usual daily activities. This includes transient laboratory test alterations.
- **Moderate:** An experience that is alleviated with simple therapeutic treatments. The experience impacts usual daily activities. Includes laboratory test alterations indicating injury, but without long-term risk.

- **Severe:** An experience that requires therapeutic intervention. The experience interrupts usual daily activities. If hospitalization (or prolongation of hospitalization) is required for treatment it becomes an SAE.

Attribution of AEs and SAEs will be categorized as:

- **Not related:** The AE is clearly not related to the study procedures (i.e., another cause of the event is most plausible and/or a clinically plausible temporal sequence is inconsistent with the onset of the event).
- **Possibly related:** An event that follows a reasonable temporal sequence from the initiation of study procedures, but that could readily have been produced by a number of other factors.
- **Related:** The AE is clearly related to the study procedures.

Reporting of AEs, SAEs, and unanticipated problems will follow the guidelines of the IU HRPP Policy on Reportable Events. Specifically, the following events will be reported promptly (i.e., within five business days) to the IRB:

- *AEs (including SAEs)* that are assessed by the PI or co-investigators as (1) unexpected, (2) related or possibly related to participation, AND (3) suggests that the research places subject(s) or others at greater risk of harm than was previously known;
- *Major protocol deviations* that may, in the opinion of the PI, (1) impact subject safety, (2) affect the integrity of the data, OR (3) affect study participant's willingness to participate in the study;
- *Noncompliance*, which includes any action or activity associated with the conduct or oversight of the research that fails to comply with federal or state regulations, institutional policies governing human study participant research, or the requirements or determinations of the IRB.

Unanticipated problems that do not meet the criteria for prompt reporting will be reported at time of protocol renewal to ensure the IRB has a full understanding of the conduct of the research.

